5.7.2.3. HI-N and HI-P Response Rate

Platelet (HI-P) and neutrophil (HI-N) response will be defined for patients with abnormal baseline values, following IWG 2006 criteria.

HI-P response will be defined for patients with baseline platelet count $< 100 \times 10^9/\text{L}$:

- For patients with baseline $\geq 20 \times 10^9/\text{L}$, an absolute mean increase of $\geq 30 \times 10^9/\text{L}$ during any rolling 8-week window on treatment;
- For patients with baseline $< 20 \times 10^9/\text{L}$, mean value of $> 20 \times 10^9/\text{L}$ and mean percentage increase $\geq 100\%$ during any rolling 8-week window on treatment.

HI-N response will be defined for patients with baseline neutrophil count (ANC) $< 1.0 \times 10^9/\text{L}$:

- Mean percentage increase $\geq 100\%$ and an absolute mean increase $> 0.5 \times 10^9/\text{L}$ during any rolling 8-week window on treatment compared with baseline.

The number and percentage of HI-N/HI-P responders will be estimated. The HI-N and HI-P response will also be listed for each patient.

5.7.2.4. Time to and Duration of HI-E Response

Time to and duration of HI-E response will be analyzed for HI-E responders only.

Time to HI-E response will be defined as the time from the first dose date to the first date of any rolling 8-week window achieving HI-E response.

Duration of HI-E response will be defined as below for LTB and HTB patients, respectively:

- a. For LTB patients, duration of HI-E response will be calculated as the longest interval during which all hemoglobin measurements having increase of ≥ 1.5 g/dL from baseline.
- b. For HTB patients, duration of HI-E response will be calculated as the time from the starting date of the first rolling 8-week window achieving response to the last date of the consecutive rolling 8-week window achieving response. When there are multiple disjoint intervals with response, the longest interval will be used.

Patients with response ongoing at the last record date will be censored. Both time to and duration of HI-E response will be analyzed as continuous variables and summarized by descriptive statistics. In addition, duration of HI-E response will also be analyzed as a time to event endpoint. The survival curves will be estimated using Kaplan-Meier method if the number of patients is more than 5.

The derivations of time to and duration of mHI-E (or HI-E) response will be listed for each patient.

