5. STATISTICAL METHODOLOGY

5.1. Definitions

Low Transfusion Burden (LTB)

LTB patients are defined as those who received < 4 units of RBCs within 8 weeks prior to Cycle 1 Day 1.

High Transfusion Burden (HTB)

HTB patients are defined as those who required ≥ 4 units of RBCs within 8 weeks prior to Cycle 1 Day 1.

Baseline Hemoglobin

Baseline hemoglobin will be an average of hemoglobin measurements within 28 days of Cycle 1 Day 1, excluding measurements within 7 days following RBC transfusion.

Baseline Transfusion Burden

Baseline transfusion burden will be calculated as the total amount of RBC transfusion during the 8 weeks prior to Cycle 1 day 1.

Baseline for Other Parameters

Baseline erythropoietin (EPO) is defined as the maximum test value within 28 days of Cycle 1 Day 1. For all other parameters, baseline is defined as the last observation on or prior to Cycle 1 Day 1.

End of Treatment (EOT)

Procedures and evaluations for the end of treatment visit should be performed on Day 113 (± 7 days) (28 days after the last dose of ACE-536).

Post Treatment Follow-Up (PTFU)

Procedures and evaluations for the post treatment follow-up visit should be performed on Day 141 (± 7 days) (28 days after EOT visit).

End of Study (EOS)

Procedures and evaluations for the end of study visit should be performed on Day 169 (± 7 days) (56 days after the Day 113/EOT visit).

Patients who discontinue treatment early should complete the end of treatment visit at the time of discontinuation and complete the post-treatment follow-up (PTFU) and EOS follow-up visits 28 days (± 7 days) and 56 days (± 7 days) after the EOT visit.

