5.7. Efficacy Analyses

The analyses for all efficacy endpoints will be performed using the ITT population.

All efficacy summaries will be presented by dose cohort for LTB and HTB patients separately. No formal hypothesis testing is planned. In addition, summaries will also be provided for the following group of patients:

- All patients in the ITT population
- Lower dose group includes patients on 0.125, 0.25 and 0.5 mg/kg dose cohorts
- Higher dose group includes patients on 0.75 mg/kg and above

- Patients in the expansion cohorts 1, 2A, 2B, and 3
- Patients in 0.125 to 0.50 mg/kg dose cohorts, and
- Patients in 0.75 to 1.75 mg/kg dose cohorts.

Efficacy Results will also be summarized with the following groups:

- All RS+ patients
- All RS- patients
- RS+ patients in the high dose (≥ 0.75 mg/kg) cohorts, and
- RS- patients in the high dose (≥ 0.75 mg/kg) cohorts.

In general, below rules apply to the derivations of efficacy endpoints related to hemoglobin and RBC transfusion data unless specified otherwise:

- Hemoglobin measurements within 7 days following RBC transfusion will be excluded from efficacy analysis
- For each patient, all efficacy endpoints will be derived based on the last dose + 56 days or the last date from transfusion record data, whichever is earlier.

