5.7.1. Primary Efficacy Endpoint

The primary efficacy endpoint is the modified erythroid response (mHI-E), defined as below:

- For low transfusion burden (LTB) patients, a hemoglobin increase of ≥ 1.5 g/dL from baseline for ≥ 14 days (in the absence of RBC transfusions). Hemoglobin measurements within 7 days following RBC transfusion will be excluded from analysis.
- For high transfusion burden (HTB) patients, a ≥ 4 units or $\geq 50\%$ reduction in RBC transfusion burden during any rolling 8-week window on treatment compared to baseline. The rolling 8-week window starts on Day 1 and increments by 1 day, e.g., from day 1 to day 56, day 2 to day 57, day 3 to day 58, etc.

A point estimate of the proportion of patients achieving a modified erythroid response will be presented along with its associated exact 95% confidence interval (CI) based on binomial distribution for LTB and HTB patients separately. The complete hemoglobin measurements and RBC transfusion records will be listed for each patient.

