5.7.2.2. HI-E Response Rate

Erythroid (HI-E) response will be defined following IWG 2006 criteria.

- For low transfusion burden (LTB) patients, a hemoglobin increase of ≥ 1.5 g/dL from baseline during any rolling 8-week in the absence of transfusion. The rolling 8-week starts and ends at a hemoglobin measurement date with duration $>= 8$ weeks.
- For high transfusion burden (HTB) patients, a reduction by ≥ 4 units of RBC transfusions during any rolling 8-week window on treatment compared to baseline.

A point estimate of the proportion of HI-E responders will be presented along with its associated exact 95% confidence interval based on binomial distribution for LTB and HTB patients separately. HI-E response will also be listed for each patient.

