5.7.2.9. Other Analysis

For the following continuous variables, the descriptive statistics including mean, median and range will be presented by dose cohort:

- Maximum reduction in transfusion burden from baseline in HTB patients
- Maximum increase in hemoglobin level from baseline in LTB patients
- Maximum mean change of hemoglobin from baseline during any rolling 8-week in LTB patients
- Maximum percentage decrease in serum ferritin
- Maximum change in absolute reticulocytes
- Change in pre-transfusion hemoglobin levels in high transfusion burden patients
- Frequency of RBC transfusions in high transfusion burden patients
- The proportion of patients with an increase of ≥ 1.0 g/dL from baseline hemoglobin maintained ≥ 8 weeks in LTB patients

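### Duration of HI-E in low transfusion burden patients has no transfusion-free condition although the HI-E response itself does, so duration can run across a later transfusion; two descriptive hemoglobin endpoints share the gap

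*SAP*

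**What the plan says.** LTB patients are not necessarily untransfused. SAP 5.1 states: "LTB patients are defined as those who received < 4 units of RBCs within 8 weeks prior to Cycle 1 Day 1". They may also be transfused on study.

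- **Response (SAP 5.7.2.2).** An LTB patient responds with a hemoglobin rise of at least 1.5 g/dL "from baseline during any rolling 8-week in the absence of transfusion", over at least 8 weeks.
- **Duration (SAP 5.7.2.4(a)).** For LTB responders, "duration of HI-E response will be calculated as the longest interval during which all hemoglobin measurements having increase of" at least 1.5 g/dL from baseline. Transfusion is not mentioned. A response still ongoing at the last record is censored, and duration is also analysed by Kaplan-Meier.
- **General rule (SAP 5.7).** "Hemoglobin measurements within 7 days following RBC transfusion will be excluded from efficacy analysis". Data are used up to 56 days after the last dose or the last date in the transfusion records, whichever is earlier.
- **Other LTB endpoints (SAP 5.7.2.9).** One is "Maximum mean change of hemoglobin from baseline during any rolling 8-week in LTB patients". Another is the proportion with a rise of at least 1.0 g/dL "from baseline hemoglobin maintained ≥ 8 weeks in LTB patients". Neither carries a transfusion condition.
- **Primary endpoint, mHI-E (SAP 5.7.1).** The rise must hold "from baseline for ≥ 14 days (in the absence of RBC transfusions"), and "Hemoglobin measurements within 7 days following RBC transfusion will be excluded from analysis".
- **Pre-transfusion values.** Protocol 12.2 asks for the hemoglobin just before every on-study transfusion. SAP 5.6.2 says these values are listed. SAP 5.2 uses all data apart from the exclusions in 5.7.

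**The concern.** Response and its duration are defined by different rules. A patient qualifies on a transfusion-free rise, but the length of that rise may then include time when donor red cells support the hemoglobin. Removing the values in the week after a transfusion does not repair this. It takes those values out and leaves the interval open, and values from day 8 onward count as continued response.

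Duration of HI-E is a stated secondary objective, and the trial has no control arm against which a transfusion-supported rise could be recognised. The omission looks unintended. Protocol 15.2.3 ties duration to the IWG 2006 criteria, the table of major changes in SAP 5.15 lists no such change, and SAP 5.10 limits its hemoglobin exposure-response analysis to patients who are transfusion-free on treatment.

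**Working it through.** The plan gives no figure for HI-E duration. The power statements in SAP 3.3 do not bear on this point. The check applies the rules as written to assumed cases.

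**1. Duration.** Inputs are the visit days in SAP 5.14.4 (weekly to Day 99, then Days 113 and 141), the 7-day exclusion in SAP 5.7, and a cut-off of Day 85 + 56 = Day 141 for a last dose on Day 85. Assume every usable value from Day 22 to Day 141 is at least 1.5 g/dL above baseline and there is one transfusion. The literal duration is 141 − 22 = 119 days wherever the transfusion falls.

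| Transfusion | Scheduled value dropped | Last scheduled value before it | Duration stopped there | Excess |
|---|---|---|---|---|
| Day 88 | Day 92 | Day 85 | 85 − 22 = 63 | 56 |
| Day 93 | Day 99 | Day 92 | 92 − 22 = 70 | 49 |
| Day 100 | none | Day 99 | 99 − 22 = 77 | 42 |
| Day 115 or 120 | none | Day 113 | 113 − 22 = 91 | 28 |

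If the interval stops on the transfusion day instead, the durations are 66, 71, 78, and 93 or 98 days.

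**2. The same case with the pre-transfusion value used.** If that value is in the data and below +1.5 g/dL, it breaks the interval under the SAP's own wording. The literal rule then gives 63, 70, 77 and 91 days, with no excess. If the value is at least +1.5 g/dL, absent, or excluded because it falls within 7 days of an earlier transfusion, 119 days stands.

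**3. The two endpoints in SAP 5.7.2.9.**
- *Rise of at least 1.0 g/dL for 8 weeks.* Assume values at or above +1.0 g/dL on Days 50 to 85, a transfusion on Day 88, and values at or above +1.0 g/dL on Days 99 and 113 only. Read literally, 113 − 50 = 63 days, which is at least 56, so the patient counts. Transfusion-free, the stretches are 85 − 50 = 35 and 113 − 99 = 14 days, so the patient does not. This again needs a pre-transfusion value that is absent or at least +1.0 g/dL.
- *Maximum rolling 8-week mean.* A low pre-transfusion value only dilutes a mean. The restriction matters only if the best window spans the transfusion. Take an assumed transfusion on Day 57 followed by changes of 1.3, 1.25, 1.2, 1.1, 1.0 and 0.8 g/dL on Days 71 to 113. The best window is Days 58 to 113, with mean 6.65/6 = 1.11 g/dL, and it is the same with or without the restriction.

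**4. Carry-over into mHI-E.** The 14 days cannot span a transfusion, but they can run from day 8 to day 22 after one. The documents give no rise per unit and no red-cell survival. Assume 1 g/dL per unit, lost linearly over L = 60 to 120 days. The residual at day 22 is units × (1 − 22/L):
- 1 unit: 0.63 to 0.82 g/dL
- 2 units: 1.27 to 1.63 g/dL, reaching 1.5 only if L is at least 88 days
- 3 units: 1.90 to 2.45 g/dL

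From a pre-transfusion value equal to baseline, 1 unit never suffices, 2 units suffice only with long survival, and 3 units suffice. At 1.0 g/dL below baseline, 3 units fail even at 120 days (1.45 g/dL). In the other direction, SAP 5.1 applies the same 7-day washout to baseline. By the same model, 2 units given 8 days before a baseline measurement raise that measurement by 2 × (1 − 8/L) = 1.73 to 1.87 g/dL, which makes response harder.

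**The case against.** The strongest objection is that the plan already contains the safeguard. Pre-transfusion hemoglobin is collected, all data are used, and the duration rule requires every measurement in the interval to be raised. A patient transfused because hemoglobin has fallen would end the interval through that value. Protocol 10.2.2 also discourages transfusion at 9 g/dL or above, and any responder with a baseline of 7.5 g/dL or more has qualifying values of at least 9.

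Much of this stands, and it limits how often the excess can occur. It does not close the gap. The SAP says only that pre-transfusion values are listed, not that they enter the derivation. Below a baseline of 7.5 g/dL, a value exactly 1.5 g/dL up is still under 9. At or above 9, Protocol 10.2.2 leaves room for symptoms and investigator discretion. After Day 99 the scheduled values are sparse: a transfusion on Day 115 removes none of them, and Day 141 then counts as continued response.

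The cut-off wording in SAP 5.7 could also be read as the date of the last transfusion. Later values would then not count, and the excess in the single-transfusion case would disappear. The wording does not settle this.

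A reader might infer that the duration rule creates responders. It cannot, because duration is analysed only in patients who have already met the transfusion-free response.

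**Conclusion.** The inconsistency is real and should be corrected. As written, LTB HI-E duration can continue across a transfusion that the response definition would not allow. In the assumed case the excess is 28 to 56 days on a literal 119. It is zero whenever a pre-transfusion value below +1.5 g/dL is used. The documents do not show how many patients would be affected. The rolling 8-week mean and the proportion with at least 1.0 g/dL for 8 weeks share the gap. Both are descriptive.

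Two stronger readings are not supported. A reader might infer that the primary endpoint is open to transfused hemoglobin in the same way. It is not: mHI-E bars transfusion during its 14 days, and the remaining carry-over depends on assumptions the documents do not supply. A reader might also infer that the net bias always favours ACE-536. The same washout at baseline can work against response, so the net direction is not established.

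**What to change.** 1. In SAP 5.7.2.4(a), require the LTB duration interval to be transfusion-free. End the response at the first RBC transfusion after response start, or at the last qualifying hemoglobin before it, and name which. State that pre-transfusion hemoglobin values enter the derivation. Clarify in SAP 5.7 what the last date from the transfusion records means.
2. In SAP 5.7.2.9, restrict the LTB maximum rolling 8-week mean change and the proportion with at least 1.0 g/dL for 8 weeks to transfusion-free windows. This aligns them with 5.7.2.2 but does not remove carry-over into a window that begins just after a transfusion. Leave the maximum hemoglobin increase as it is: limiting it to values before any on-study transfusion would discard nearly all follow-up for a patient transfused early.
3. Optionally, keep the 7-day rule for the main mHI-E analysis, add a sensitivity analysis with a longer post-transfusion exclusion, and report how many LTB responders change status.

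The cost is SAP wording and programming, since transfusion dates and hemoglobin are already collected. LTB durations may become slightly shorter. Ending the response at any transfusion also treats one given for reasons unrelated to lost response as an end of response, which the SAP should acknowledge.

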### 15.2.3. Secondary Analysis

**Safety analysis:** To assess clinical safety, adverse events, vital sign measurements and clinical laboratory information will be summarized. Adverse Events will be coded using the Medical Dictionary for Regulatory Activities (MedDRA). Changes from baseline for clinical laboratory values and vital signs will be summarized over time. Descriptive statistics and shift tables will be generated as appropriate.

**Secondary efficacy/pharmacodynamic analysis** of the study will be performed using the ITT and EE populations and will include:

- Modified erythroid response (mHI-E), as described above for primary endpoint, performed using the ITT population.
- HI-E response rate as defined by IWG 2006 criteria ([Appendix 5](#)). Improvements must last  $\geq$  8 weeks. For non-transfusion dependent patients, an increase of  $\geq 1.5$  g/dL from pre-treatment hemoglobin. For transfused patients, a reduction by  $\geq 4$  units of RBCs transfused (for a hemoglobin  $\leq 9.0$  g/dL) during any 8-week period on study, compared with the 8-week period prior to Cycle 1 Day 1.
- Time to mHI-E and HI-E response and duration of mHI-E and HI-E response as per the IWG 2006 criteria.
- Frequency of RBC transfusion, and rate of RBC transfusion independence in transfusion dependent patients.
- Other pharmacodynamic (PD) endpoints including:
  - Biomarkers for iron metabolism
  - Biomarkers for bone metabolism
  - Relationship of biomarkers to response
  - Rates of HI-N and HI-P

**Exploratory endpoints** will include:

- Evaluation of biomarkers related to the TGF $\beta$  superfamily.
- Evaluation of self-reported quality of life in the expansion cohort using tools including but not limited to the FACT-An questionnaire.

All binary endpoints will be summarized using both a point estimate and its exact confidence interval based on the binomial distribution. The time-to-event type secondary endpoints will be analyzed using Kaplan-Meier method to estimate the survival curve and median time to event and 95% confidence interval.

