5.7.2. Secondary Efficacy Endpoints

5.7.2.1. RBC Transfusion Independence

For patients with ≥ 2 units of RBC transfusion at baseline, RBC transfusion independence (RBC-TI) response is defined as not requiring RBC transfusion for more than 8 weeks while on treatment.

The proportion of RBC-TI responders will be estimated by a point estimate along with the exact 95% confidence interval based on binomial distribution. The denominator is the number of patients with ≥ 2 units of RBC transfusion at baseline.

Time to RBC-TI will be defined the time from the first dose date to the starting date of the first consecutive 8-week window not requiring RBC transfusion. Duration of RBC-TI will be

calculated as the longest period of time not requiring RBC transfusion during treatment and will be censored at the last record date for ongoing responses.

Both time to and duration of RBC-TI will be analyzed as continuous variables and summarized by descriptive statistics for RBC-TI responders only. Duration of RBC-TI will also be analyzed as a time to event variable using Kaplan-Meier method.

The derivations of RBC-TI response, time to and duration of RBC-TI will be listed for each patient.

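### Durations of HI-E and RBC-TI are censored when ongoing, yet also summarised by plain means and medians with no rule for the censored values

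*SAP*

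**What the plan says.** For HI-E, SAP 5.7.2.4 sets the population: "Time to and duration of HI-E response will be analyzed for HI-E responders only". For duration it then gives three instructions.

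- Censoring: "Patients with response ongoing at the last record date will be censored".
- Descriptive summary: "Both time to and duration of HI-E response will be analyzed as continuous variables and summarized by descriptive statistics". Under SAP 5.2, descriptive statistics mean n, mean, standard deviation, minimum, median and maximum.
- Time-to-event analysis: "In addition, duration of HI-E response will also be analyzed as a time to event endpoint", followed by "The survival curves will be estimated using Kaplan-Meier method if the number of patients is more than 5".

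For RBC-TI, SAP 5.7.2.1 says that duration "will be censored at the last record date for ongoing responses", and also "Both time to and duration of RBC-TI will be analyzed as continuous variables and summarized by descriptive statistics for RBC-TI responders only". It adds a Kaplan-Meier analysis of duration. That section sets no minimum number, but SAP 5.2 applies the more-than-5 condition to Kaplan-Meier curves in general.

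SAP 5.7 ends each patient's efficacy data at the last dose plus 56 days, or at the last transfusion-record date if earlier. It presents efficacy by dose cohort for low and high transfusion burden (LTB, HTB) separately, and also in several pooled groups.

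Time to HI-E has only the responder-only descriptive summary. Protocol 15.2.3 lists it among the secondary endpoints and says: "The time-to-event type secondary endpoints will be analyzed using Kaplan-Meier method to estimate the survival curve and median time to event", with a 95% CI.

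**The concern.** A censored duration is a lower bound. A mean that takes it as an observed value is too low, and a mean that leaves it out loses the longest responses. The SAP defines the censoring and then asks for a summary that has no place for it, so the programmer must choose and the reader of the table cannot tell which choice was made.

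Duration of response is one of the results that readers of an ascending-dose study will compare across cohorts. If many responses are ongoing at the cut-off, the plain mean reflects the length of follow-up more than the persistence of the effect. The risk is greatest in small cells, where no curve is planned beside it.

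Time to HI-E raises a lesser issue. A responder-only summary conditions on the outcome, so it says nothing about how many patients responded.

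**Working it through.** The plan states no figure for duration, so there is none to reproduce. The checks below use the plan's dates and stated assumptions.

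**1. Observation limit.** The last possible dose is on Day 85 ± 2 (Protocol 10.1) and the cut-off is last dose + 56 days (SAP 5.7). 85 + 56 = Day 141. No duration can exceed about 141 days, and an 8-week response must begin by Day 141 − 55 = Day 86. An earlier last dose brings the cut-off forward.

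**2. Plain mean, censored values taken as observed.** Assume onset on Day 22 and duration = 56 days + exponential with mean *m*. The longest observable duration is 141 − 22 = 119 days, so the observable excess over 56 days is 63 days.

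- Censored share = exp(−63/*m*)
- Plain mean = 56 + *m*(1 − exp(−63/*m*))
- True mean = 56 + *m*

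| *m* | Censored | Plain mean | True mean | Understatement |
|---|---|---|---|---|
| 56 days (8 weeks) | exp(−1.125) = 32% | 56 + 56 × 0.675 = 94 | 112 | 16% |
| 182 days (26 weeks) | exp(−0.346) = 71% | 56 + 182 × 0.293 = 109 | 238 | 54% |

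**3. Plain mean, censored values dropped.** The mean is then 56 + *m* − 63 × exp(−63/*m*)/(1 − exp(−63/*m*)). For *m* = 56 this is 56 + 56 − 63 × 0.325/0.675 = 82 days. For *m* = 182 it is 56 + 182 − 63 × 0.707/0.293 = 86 days. Both are further from the truth than in step 2.

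**4. Median.** The true median is 56 + *m* ln 2. For *m* = 56 it is 95 days, below the 119-day limit, so the plain median from step 2's rule is correct. For *m* = 182 it is 182 days, above the limit, so the plain median sits at 119. A simulation of 100,000 responders, with onset uniform on Days 1 to 43 and cut-off at Day 141, gives the same pattern:

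| True median (days) | Censored | Plain median | Kaplan-Meier median |
|---|---|---|---|
| 70 | 5% | 70 | 70 |
| 84 | 21% | 84 | 84 |
| 112 | 46% | 103 | 112 |
| 168 | 68% | 111 | not reached |
| 364 | 87% | 117 | not reached |

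**5. Where a curve would be available.** The analysis is in responders, so the more-than-5 condition is read as at least 6 responders. Taking the 30% response rate of SAP 3.3, the binomial chance of at least 6 responders is:

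- 6 patients (largest escalation cohort): 0.3^6 = 0.07%
- 9 patients (treated in expansion cohort 3, SAP 3.1): 2.5%
- 10 patients (minimum per stratum in expansion cohort 1): 4.7%
- 15 patients: 28%
- 25 patients (target for each of 2A and 2B): 81%, before any LTB/HTB split

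So at that rate curves are likely mainly in 2A, 2B and the pooled groups.

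**6. Time to HI-E.** Assume onset uniform on Days 1 to 86, the same at every response rate. The responder-only median is then about 43 days at response rates of 10%, 30%, 50% and 60%. A Kaplan-Meier median in all patients, with non-responders censored at Day 141, is not reached at 10%, 30% and 50%, and is about 72 days at 60%. The constant 43 follows from the assumption. It shows only that the summary carries no information on the response rate.

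**The case against.** The strongest reply is that the SAP already plans the right analysis. The sentence after the descriptive summary adds a time-to-event analysis of HI-E duration, and 5.7.2.1 does the same for RBC-TI. A reader of the descriptive sentence alone might infer that censoring is ignored altogether, and that is not so. The SAP does not rank the two summaries, it plans efficacy summaries in pooled groups where more than 5 responders are plausible, and it lists every patient's derivation. This stands, and it confines the problem to the plain summaries.

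A reader might also infer that the SAP instructs that censored values be taken as complete. It does not say so. That is the natural reading, because duration is defined as an observed interval, but the provable fault is a missing rule. Step 3 shows that the other obvious choice does not rescue the mean.

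The size rests on assumptions. Neither the Day 22 onset nor the exponential means come from the documents. The phase 1 half-life of 15.5 to 18.5 days (Protocol 7.3) makes 56 days about 3.0 to 3.6 half-lives (56/18.5 and 56/15.5), so many responses may have ended by the cut-off. Kaplan-Meier would not recover a mean of 238 days either, because with 71% censored its median would not be reached.

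On time to HI-E, a responder-only summary is common and is openly labelled, and response rates are reported by LTB and HTB alongside. A reader might infer an undeclared departure from the protocol, because SAP 5.15 does not list the change. That cannot be confirmed. The SAP follows amendment 06, whereas the supplied protocol has no expansion cohort 3 and a planned total of 128 against the SAP's 153. Its Kaplan-Meier sentence is also generic and does not name time to HI-E or its risk set.

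**Conclusion.** The point holds for the plain summaries of duration. HI-E and RBC-TI durations are censored and also averaged, with no rule for the censored values. Under the stated assumptions the plain mean is 16% to 54% too low if censored values enter as observed, and lower still if they are dropped. The plain median is sound at low censoring and flattens when censoring is heavy: about 103 to 117 days for true medians of 112 to 364 days in the simulation. How much censoring will occur cannot be derived from the documents.

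The effect matters most where 5 or fewer responders leave the plain figures as the only summary statistics. The documents do not support saying that the SAP lacks a censoring-aware analysis of duration, or that its handling of time to HI-E is a proven undeclared change. These are descriptive secondary endpoints with no hypothesis testing, and the primary mHI-E proportion is unaffected.

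**What to change.** In SAP 5.7.2.1 and 5.7.2.4:

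- Report duration of HI-E and RBC-TI by Kaplan-Meier, with median, 95% CI and number censored, in the pooled groups and in cohorts with more than 5 responders.
- Elsewhere, list individual durations with a censoring mark, and omit the plain mean and median.
- State that the more-than-5 condition counts responders.

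As a secondary change, label the time-to-HI-E summary as conditional on response. Add, as a supplement, a Kaplan-Meier or cumulative-incidence estimate in all ITT patients. Check amendment 06, and if it keeps the protocol's Kaplan-Meier sentence, list the change in SAP 5.15.

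The cost is SAP wording and small table changes, with no new data. Some medians will be shown as not reached, which is what the data would support.
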